7.5.5.1 Capillary Leak Syndrome and Associated Symptoms

CLS is associated with vascular endothelial injury related to fusion protein administration and may occur 3 – 8 days after initiation of treatment.

Patients may exhibit symptoms of **hypotension**, fluid overload, evidenced by **weight gain** or edema, nausea, and anorexia, shortness of breath and, at times, confusion and muscle injury. Findings may include **hypoalbuminemia**, reductions in blood oxygen saturation, and evidence of pulmonary edema on chest x-ray. **These symptoms may present individually or as part of CLS.**

Refer to Section [7.5.5.1.1](#), Section [7.5.5.1.2](#), and Section [7.5.5.1.3](#) for the management of the individual symptoms of hypotension, increase in body weight, and hypoalbuminemia. If the constellation of symptoms is considered to be potentially representative of CLS, the patient is to be managed as described in Section [7.5.5.1.4](#).

7.5.5.1.1 Symptomatic Hypotension

Withhold SL-401 for patients with a systolic blood pressure (BP) ≤ 80 mmHg.

Symptomatic hypotension is to be treated with a bolus of normal saline or its equivalent at the discretion of the investigator, with SL-401 held (postponed) until resolution.

During the dosing period, if BP fails to improve with boluses of fluids totaling 1 liter of normal saline or its equivalent, further standard measures to correct the BP will be undertaken; regardless of the rapidity or delay in resolution, SL-401 will be withheld on that day. If hypotension persists such that further treatment is not feasible during the day of the intended dose and the following day, no further SL-401 will be administered to the patient for that cycle.

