7.5.5 Dose Delays/Modifications and Management Procedures for Toxicities Associated with SL-401

During the dosing period for each cycle, individual SL-401 infusions may be delayed to allow for toxicity resolution.

If dosing is resumed within a cycle, any subsequent doses in that cycle must be administered within the first 10 days of that cycle; thus, patients may receive fewer than 5 doses during a given study cycle. SL-401 may be resumed at the same dose or a reduced dose for Grade 3/4 toxicities (see [Table 3](#) and Section [7.5.5.11](#)).

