15.5 Appendix E. CLS Management Guidance

CLS Element	Time of Presentation	Recommended Action	SL-401 Dosing Management
Serum albumin <3.2 g/dL (without albumin supplementation)	Prior to 1 st SL-401 administration	Do not dose (patient not eligible for participation)	
Serum albumin <3.5 g/dL OR reduced by ≥0.5 g/dL from pre-dose value (with or without albumin supplementation) A pre-dose body weight that is increased by ≥1.5 kg over the previous day's pre-dose weight	During SL-401 dosing ¹	
 • For the CLS element of albumin decrease: 
 ▪ Administer albumin 25 g IV (q12h or more frequently as practical) until serum albumin is both ≥3.5 g/dL and not reduced by ≥0.5 g/dL from pre-dose value • For the CLS element of body weight increase: 
 ▪ Administer albumin 25 g IV (q12h or more frequently as practical), and manage fluids and blood pressure, as clinically indicated, until body weight increase has resolved (i.e. the increase is no longer greater than 1.5 kg from the previous day's pre-dose weight) 	
 • Hold SL-401 dosing until the relevant CLS element has resolved as specified by Recommended action²
Edema, fluid overload and/or hypotension		
 • Administer albumin 25 g IV (q12h, or more frequently as practical) until serum albumin is ≥3.5 g/dL • Administer 1 mg/kg of methylprednisolone (or an equivalent) per day, until resolution of CLS element or as clinically indicated • Aggressive management of fluids status, which could include intravenous fluids and/or diuretics, until resolution of CLS element or as clinically indicated 	

1. For patients eligible for treatment with SL-401 with serum albumin >3.2 g/dL but <3.5 g/dL on the day of dosing, IV albumin (25 g) is recommended prior to administration of SL-401 to increase the serum albumin to ≥3.5 g/dL before the 1st dose of SL-401.
2. SL-401 administration may resume in the same cycle if all CLS elements have resolved and the patient did not require measures to treat hemodynamic instability. SL-401 administration should be held for the remainder of the cycle if CLS elements have not resolved or the patient required measures to treat hemodynamic instability (even if resolved), and SL-401 administration may only resume in the next cycle if all CLS elements have resolved, and the patient is hemodynamically stable.

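### For isolated hypotension that fails 1 L of fluid, needs further measures and resolves by the next day, Protocol 7.5.5.1.1 by implication allows same-cycle re-dosing, whereas Appendix E footnote 2, read naturally, does not

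*Protocol*

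**What the plan says.** Protocol 7.5.5.1 sets up two routes. Hypotension, weight gain and low albumin that occur singly are managed under 7.5.5.1.1 to 7.5.5.1.3. A combination that might represent CLS is managed under 7.5.5.1.4.

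On the single-symptom route, 7.5.5.1.1 covers the patient whose BP fails to improve after boluses totalling 1 L: "further standard measures to correct the BP will be undertaken; regardless of the rapidity or delay in resolution, SL-401 will be withheld on that day". The next sentence sets the condition for stopping the cycle: "If hypotension persists such that further treatment is not feasible during the day of the intended dose and the following day, no further SL-401" is to be given in that cycle. The general rule in 7.5.5 provides for restarting: "If dosing is resumed within a cycle, any subsequent doses in that cycle must be administered within the first 10 days of that cycle".

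Appendix E (section 15.5) has a row for "Edema, fluid overload and/or hypotension". It directs IV albumin, daily methylprednisolone and "Aggressive management of fluids status, which could include intravenous fluids and/or diuretics, until resolution of CLS element or as clinically indicated". Footnote 2 then states that "SL-401 administration should be held for the remainder of the cycle if CLS elements have not resolved or the patient required measures" for instability; the full trigger is that "the patient required measures to treat hemodynamic instability (even if resolved"). After that, "SL-401 administration may only resume in the next cycle if all CLS elements have resolved, and the patient is hemodynamically stable".

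Sections 7.5.5.1.2 (weight gain) and 7.5.5.1.4 (CLS) refer the reader to Appendix E. Section 7.5.5.1.1 does not.

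**The concern.** A site managing hypotension as a single symptom would turn to 7.5.5.1.1. It would find a hold for the day, with a cycle stop that depends on persistence into the next day. A site that opened Appendix E would find a cycle stop that depends on the treatment needed, whether or not the episode has resolved. The same patient could be dosed the next day at one centre and held until the next cycle at another; the synopsis allows up to 20 centres.

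This is a safety question. CLS was the principal DLT in Study 50047 (Protocol 3.6.3) and was a serious adverse event in 2 of 26 BPDCN patients in Study STML-401-0114 (Protocol 3.6.2). A site using only 7.5.5.1.1 would also not be pointed to the albumin and steroid actions that Appendix E gives for hypotension.

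**Working it through.** The plan states no figure to reproduce. The check applies each text to one scenario and then counts the doses that turn on the answer.

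**Scenario.** Hypotension during the dosing period, managed as an individual symptom. BP does not improve after 1 L of fluid, further BP measures are given, and the episode has resolved by the next day, before Day 10.

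**Applying the texts**

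1. *7.5.5.1.1.* SL-401 is withheld that day. The two-day condition is not met, so the cycle is not stopped. Nothing in the section expressly permits dosing the next day. The permission follows from those limits together with 7.5.5.
2. *Appendix E, footnote 2.* Hypotension is a listed element, and the and/or wording lets it qualify alone. If BP measures beyond 1 L of fluid count as treating hemodynamic instability, the hold runs to the end of the cycle and resolution does not lift it.
3. *7.5.5.1.4.* It agrees with footnote 2, but applies when the picture is considered potentially CLS, so it does not settle the single-symptom case.
4. *7.5.5.9.* It holds clinically significant Grade 3/4 toxicity for the current cycle. Its heading limits it to other toxicities, yet its exceptions point back to the albumin, transaminase and creatinine sections. It may therefore reach Grade 3/4 hypotension. It does not reach lower grades.
5. *Table 3 in 7.5.5.10.1.* It excludes toxicities covered in 7.5.5.1 to 7.5.5.8, so it does not help.

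**Doses that depend on the choice.** Inputs: 5 doses per cycle on consecutive days, all to be completed by Day 10 (7.5.2, 7.5.5). Assumption: no interruption before an episode on Day k.

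- Episode before the Day k infusion: k − 1 doses given, so 5 − (k − 1) = 6 − k remain. Restarting on Day k + 1, the last falls on Day k + (6 − k) = Day 6, within the limit.
- Episode after the Day k infusion: k doses given, so 5 − k remain, ending on Day 5.

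| Day k | Pre-dose: 6 − k (share of 5) | Post-infusion: 5 − k (share of 5) |
|---|---|---|
| 1 | not applicable (no dose yet given) | 4 (80%) |
| 2 | 4 (80%) | 3 (60%) |
| 3 | 3 (60%) | 2 (40%) |
| 4 | 2 (40%) | 1 (20%) |
| 5 | 1 (20%) | 0 (0%) |

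Both columns are needed because 7.5.4 schedules vital signs before each infusion, at its end, and 30, 60 and 240 minutes afterwards. The range is 0 to 4 doses per affected cycle.

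**The case against.** The best defence is that the texts govern different patients: isolated hypotension follows 7.5.5.1.1, while possible CLS follows 7.5.5.1.4 and Appendix E, which is titled CLS guidance and says what should be done. This does not hold up well. Appendix E works element by element, admits hypotension alone, and is cited in 7.5.5.1.2 for weight gain managed as a single symptom.

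Other parts of the defence stand:

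- The conflict rests on two inferences: that 7.5.5.1.1 permits re-dosing, and that its further measures are what footnote 2 means. The footnote's trigger is not defined.
- In the extracted table the dosing cell beside the hypotension row is blank and the footnote marker sits by the albumin and weight row. This is probably a merged cell. The footnote itself speaks of all CLS elements.
- Other controls remain: vital signs before each infusion, withholding at systolic BP of 80 mmHg or below and until symptomatic hypotension resolves, and possibly 7.5.5.9 for Grade 3/4 episodes.
- SAP 3.1 gives enrolment at database lock (18 in Stage 1, 9 in Stage 2), and Protocol 6.4 says data entry generally closes before lock. The documents do not say that dosing has ended, but few or no doses may remain.

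A reader might also apply the CLS onset window in 7.5.5.1 (3 to 8 days after starting) and conclude that 1 to 3 doses are typically at stake. The documents do not support that. The window describes CLS, the scenario is hypotension not judged to be CLS, and a post-infusion episode on Day 5 leaves no dose.

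**Conclusion.** The inconsistency is real but narrow. It concerns hypotension managed as an individual symptom that fails 1 L of fluid, needs further BP measures and resolves by the next day. It is clearest below Grade 3. It is worth correcting because the protocol's own CLS guidance is the stricter text. Confidence is medium, since one side of the conflict is implied and the other turns on an undefined phrase.

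The size is 0 to 4 of 5 doses in an affected cycle, assuming uninterrupted dosing before the episode. This counts doses and does not measure harm. The documents give no rate for this kind of episode, so no number of patients can be stated.

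Two stronger readings should be resisted. A reader might infer that the protocol expressly authorises next-day dosing after unstable CLS. It does not: 7.5.5.1.4 bars same-cycle resumption there, and the permission in 7.5.5.1.1 is only implied. A reader might also infer that DLT counts, the MTD or error rates are compromised. Nothing in the documents shows that. The DLT definition in 6.2.1.1 does not refer to these holding rules, and Grade 3 or higher hypotension is not among its named exceptions.

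**What to change.** Four linked edits:

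1. In 7.5.5.1.1, state that when BP fails to improve with 1 L of fluid and further measures are required, SL-401 is held for the rest of that cycle. It restarts only in the next cycle, once all CLS elements have resolved and the patient is hemodynamically stable.
2. Add a cross-reference there to Appendix E for albumin, steroid and fluid management.
3. In Appendix E, state that the footnote 2 trigger includes BP measures beyond 1 L of fluid. Whether boluses up to 1 L alone should count is a clinical decision for the sponsor, since Appendix E lists intravenous fluids among its own actions for this row.
4. Reword the two-day persistence sentence so that it applies only to hypotension not requiring such measures. It would then govern few cases, because 7.5.5.1.1 already calls for further measures once 1 L fails.

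The clinical cost is the remaining doses of the affected cycle, 0 to 4 by the count above, which footnote 2 already says to hold. The administrative cost is a short amendment and the IRB/IEC submission that 13.5 requires for changes affecting patient safety. No new data collection or SAP output is needed. If no dosing remains in this trial, the value lies in any later protocol that reuses the text.

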7.5.5.1.2 Increase in Body Weight

Withhold SL-401 infusion if body weight increases by ≥ 1.5 kg over pre-treatment weight on the previous treatment day.

Patients with an increase in body weight of ≥ 1.5 kg from the previous day may be treated with fluid restriction and/or diuretics (e.g., furosemide), as clinically indicated, and should also receive albumin 25 g IV daily or every 12 hours as clinically feasible until weight gain has resolved, as indicated in [Appendix E](#). Dosing within a cycle may resume only if ≥ 1.5 kg weight gain has resolved. If dosing is resumed, any subsequent doses in that cycle must be administered within the first 10 days of that cycle.

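### Appendix E's test for resolved weight gain conflicts with Section 7.5.5.1.2 at exactly 1.5 kg, and after a held dose its reference day is unclear

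*Protocol*

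**What the plan says.** Protocol Section 7.5.5.1.2 opens with a stand-alone instruction to withhold the infusion when weight is up by 1.5 kg or more "over pre-treatment weight on the previous treatment day". Its second paragraph changes the comparison: patients with that gain "from the previous day may be treated with fluid restriction" and/or diuretics, and should receive albumin "as clinically feasible until weight gain has resolved, as indicated in" Appendix E. It then states the restart condition: "Dosing within a cycle may resume only if ≥ 1.5 kg weight gain has resolved". No reference day is repeated there.

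Appendix E has its own hold criterion, "A pre-dose body weight that is increased by ≥1.5 kg over the previous" day's pre-dose weight. Its recommended-action column treats the gain as resolved when "the increase is no longer greater than 1.5 kg from the previous" day's pre-dose weight. Its dosing column holds SL-401 until the element has resolved as that column specifies, so this test governs restart. Footnote 2 adds "SL-401 administration may resume in the same cycle if all CLS elements have resolved" and no measures for hemodynamic instability were needed.

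Three other places bear on the point:

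- Section 7.5.3.2 uses body weight to one decimal place for the dose calculation.
- Sections 9.3.1 and 9.4.1 schedule a pre-infusion weight on dosing days, running up to Day 10 if infusions are held.
- Section 7.5.5.1 describes "fluid overload, evidenced by" weight gain or edema among the signs of capillary leak syndrome (CLS), and sends weight gain to Section 7.5.5.1.2 when it is managed as an individual symptom.

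**The concern.** A hold rule and its release rule should be complements: whatever is held is not resolved, and the reverse. The albumin rule in the same Appendix E row has that form. It holds below 3.5 g/dL or at a fall of 0.5 g/dL or more, and counts as resolved at 3.5 g/dL or above with no such fall remaining. The weight rule does not have that form, and its reference day is not tied down once a dose has been skipped.

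What is at stake is dosing safety and consistency between sites. Section 3.6.3 names CLS as the principal DLT of Study 50047 and lists withholding for weight increases as an added precaution in this trial. Section 7.5.5.1 puts CLS onset at 3 to 8 days after treatment starts, which lies inside the 10-day window in which held doses may resume. If one site compares with the last dosed day and another with yesterday's weight, a patient with persisting fluid gain could stay on hold at the first and meet the Appendix E weight test at the second. Because weight gain may be managed without a CLS diagnosis, the weight rule needs to be clear on its own.

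**Working it through.** The plan gives no figure to reproduce, so the rules are set side by side and applied to example weights.

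| Rule | Threshold | Reference weight |
|---|---|---|
| 7.5.5.1.2, withhold | gain ≥ 1.5 kg | previous treatment day |
| 7.5.5.1.2, supportive care | gain ≥ 1.5 kg | previous day |
| 7.5.5.1.2, resume | gain of ≥ 1.5 kg has resolved, i.e. gain < 1.5 kg | not restated |
| Appendix E, hold | gain ≥ 1.5 kg | previous day's pre-dose weight |
| Appendix E, resolved | gain not > 1.5 kg, i.e. ≤ 1.5 kg | previous day's pre-dose weight |

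On consecutive dosing days the previous treatment day and the previous day are the same, so the references differ only after a held dose.

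Assumed weights, recorded to 0.1 kg: Day 1 70.0 kg (dosed); Day 2 72.0 kg (+2.0 kg, held). Let W be the Day 3 pre-dose weight.

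**Body text.** Dosing is barred if W − 70.0 ≥ 1.5, so W ≥ 71.5 kg.

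**Appendix E, reference fixed at 70.0 kg** (read as the last dosed day, or as the comparison that triggered the hold). Resolved if W − 70.0 ≤ 1.5, so W ≤ 71.5 kg. The overlap with the body-text bar is the single value 71.5 kg. There Appendix E's own hold criterion is also met, since 1.5 ≥ 1.5.

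**Appendix E, calendar-day reference of 72.0 kg.** Resolved if W − 72.0 ≤ 1.5, so W ≤ 73.5 kg.

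- Overlap with the bar: 71.5 to 73.5 kg, (73.5 − 71.5)/0.1 + 1 = 21 recordable weights.
- At 73.5 kg the Appendix E hold also fires (73.5 − 72.0 = 1.5). That leaves 71.5 to 73.4 kg, 20 weights, at which the two texts give plainly opposite answers.
- Plateau example, W = 72.0 kg: the body text sees 72.0 − 70.0 = +2.0 kg (hold); Appendix E sees 72.0 − 72.0 = 0.0 kg (resolved).
- Upper end: 73.5 kg is +3.5 kg over the last dosed day and still passes the Appendix E resolution test.

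**Dependence on the assumed held-day gain.** If Day 2 is g kg above Day 1, Appendix E resolves up to 70.0 + g + 1.5, so the overlap is g/0.1 + 1 weights. For g = 2.0 this is 21; for g = 1.5 (Day 2 at 71.5 kg) it is 71.5 to 73.0 kg, or 16 weights, 15 of them plainly opposite. The one-value conflict under a fixed reference does not depend on g.

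**After the proposed change** (reference 70.0 kg, hold at ≥ 1.5, resume at < 1.5): 71.5 kg is held and not resolved; 72.0 kg is held; the highest weight at which dosing may resume is 71.4 kg. Both texts then agree at every weight.

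**The case against.** The strongest reply is that the body text already settles the matter. Its first sentence withholds without condition against the previous treatment day, which bars dosing in the example at 72.0 kg whatever Appendix E says. Appendix E is titled as guidance, and Section 7.5.5.1.4 calls it a summary. The fluid-overload row and footnote 2 may also block the dose. At exactly 1.5 kg on a fixed reference, Appendix E's own hold still applies, so the overlap does not by itself release a dose.

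The calendar-day reading can also be called strained. The increase most naturally means the one that triggered the hold, and a pre-dose weight is an odd term for a day without a dose. Scheduling a weight on held days does not make it the new reference. Finally, the count of 21 follows from an assumed 2.0 kg gain and is not a frequency.

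Much of this stands. These provisions limit the consequence, and the counts are illustrations that grow with the assumed gain. The replies do not make the texts agree, however. Section 7.5.5.1.2 itself moves from the previous treatment day to the previous day and cites Appendix E beside the words on resolution. Appendix E contains the only spelled-out definition of a resolved gain, and its dosing column ties restart to it. Nothing in either place says which weight applies after a held dose. The extra conditions in Section 7.5.5.1.4 (discussion with the Medical Monitor, no dosing on the day an abnormality is identified) concern CLS and do not cover isolated weight gain.

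**Conclusion.** The concern holds, as a minor one. The conflict at exactly 1.5 kg is explicit on any reading: Appendix E contradicts itself there and contradicts Section 7.5.5.1.2. With a fixed reference it affects one recordable weight. The reference-day problem is an ambiguity. Read as the last dosed day or the triggering comparison, the two texts share a reference. Read as the calendar day, they conflict over a range of weights (21 in the example, 16 if the held-day gain is 1.5 kg), including that of a patient who has simply stayed 2.0 kg up.

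The sizes rest on assumed weights recorded to 0.1 kg. The documents do not say how often a hold for weight occurred or how sites resolved it. No effect on DLT counts or on any planned analysis is shown.

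**What to change.** In Appendix E (hold criterion and resolution text) and in the second paragraph of Section 7.5.5.1.2, use one reference for both hold and resumption: the pre-dose weight on the last day SL-401 was actually given in that cycle. Hold at a gain of ≥1.5 kg and resume only at <1.5 kg. The first sentence of Section 7.5.5.1.2 can stay as it is.

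The cost is wording in two places, or a clarification letter, with no new measurements. The downside is that some holds within the 10-day window will be longer.

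SAP Section 3.1 already reports enrolment at database lock (18 patients in Stage 1, 9 in Stage 2), so rewording may come too late for those patients. For them, the study report should state which resumption rule sites applied. The documents do not show that this was recorded: Section 7.5.5.11 requires reasons for dose modifications only. If it cannot be recovered, the report should say so.

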7.5.5.1.3 Hypoalbuminemia

Patients are to have serum albumin measurements performed daily until completion of SL-401 administration.

- In settings in which albumin is reduced to 3.0-3.5 g/dL (30-35 g/L) or by ≥ 0.5 g/dL (5 g/L) below the level at the start of the cycle, withhold SL-401 infusion and administer albumin 25 g IV daily or every 12 hours as clinically feasible until serum albumin is both ≥ 3.5 g/dL and not reduced by ≥ 0.5 g/dL from the level at the start of the cycle prior to resuming treatment with SL-401 in the same cycle.
- In settings in which albumin is reduced to <3.0 g/dL (30 g/L) or by more than 1.0 g/dL (10 g/L) below the level at the start of the cycle (i.e., from 4.3 g/dL to 3.2 g/dL), withhold SL-401 infusions for the duration of that particular cycle. Albumin should be administered until the albumin level is at least above 3.5g/dL. Consultation with the medical monitor is advised.
- Dosing in the next cycle may resume if albumin remains at 3.5 g/dL without additional albumin infusions.

Albumin infusions are supportive measures, and are not intended to enable treatment in settings in which hypoalbuminemia would otherwise preclude SL-401 administration.

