7.5.5.1.4 Capillary Leak Syndrome

Withhold SL-401 infusion for patients with clinical signs and symptoms consistent with CLS.

If CLS is identified, 1 mg/kg/day of methylprednisolone (or an equivalent) should be administered until resolution or as clinically indicated along with administration of albumin as specified in [Appendix E](#).

Ongoing CLS or CLS with clinical/hemodynamic instability

SL-401 administration during the cycle may not resume if there are signs or symptoms of CLS along with evidence of hemodynamic instability, significant clinical deterioration or changes in albumin, defined as a decrease to <3.0 g/dL or reduction by >1.0 g/dL from the start of the cycle or CLS elements have not resolved.

SL-401 administration may only resume in the next cycle if all CLS elements have resolved, and the patient is hemodynamically stable and laboratory values have recovered to a level that permits dosing.

CLS without clinical/ hemodynamic instability

In the setting of signs/symptoms of CLS that DID NOT include hemodynamic instability OR significant clinical deterioration OR reductions in albumin that would prevent further dosing, SL-401 administration in that cycle may be delayed and resume if there is no evidence of ongoing CLS, pending discussion with the study Medical Monitor.

Any subsequent SL-401 is to be administered on days *subsequent* to the identification of the abnormality (not the same day). If dosing is resumed, any subsequent doses in that cycle must be administered within the first 10 days of that cycle. SL-401 administration in subsequent cycles may resume per the normal schedule after Day 28 of the previous cycle.

Also see [Appendix E](#) for summary of recommended actions.

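### Appendix E leaves out the albumin stop in Protocol Section 7.5.5.1.3, so read alone it permits same-cycle re-dosing that the body text bars

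*Protocol*

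**What the plan says.** Protocol Section 7.5.5.1.3 sets two tiers during dosing.

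- **Milder tier:** albumin of 3.0 to 3.5 g/dL, or a fall of at least 0.5 g/dL from the start of the cycle. SL-401 is held and IV albumin given. Dosing may resume in the same cycle once albumin is at least 3.5 g/dL and is no longer down by 0.5 g/dL or more.
- **Stricter tier:** albumin below 3.0 g/dL, or a fall of more than 1.0 g/dL. Sites "withhold SL-401 infusions for the duration of that particular cycle", and consultation with the Medical Monitor is advised.

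The section closes by saying that albumin infusions "are not intended to enable treatment in settings in which hypoalbuminemia would otherwise preclude SL-401 administration". Section 7.5.5.1.4 repeats the stricter tier for patients with signs of CLS: dosing may not resume in the cycle after "changes in albumin, defined as a decrease to <3.0 g/dL or reduction by >1.0 g/dL from the start of the cycle".

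Appendix E has one on-treatment albumin row: "Serum albumin <3.5 g/dL OR reduced by ≥0.5 g/dL from pre-dose value". The action is to infuse albumin until both recovery conditions are met, holding SL-401 until then. Under footnote 2, SL-401 "may resume in the same cycle if all CLS elements have resolved and the patient did not require measures to treat hemodynamic instability". It "should be held for the remainder of the cycle if CLS elements have not resolved or the patient required measures to treat hemodynamic instability", whether or not that instability has since resolved. Neither the 3.0 g/dL limit nor the 1.0 g/dL fall appears anywhere in Appendix E.

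**The concern.** Appendix E gives the rule for resuming but not the rule for stopping. Its single row covers every albumin value below 3.5 g/dL, including those for which the body text ends the cycle. Recovery is reached by infusing albumin, so in the stricter tier the table lets infusion do what Section 7.5.5.1.3 says it is not meant to do.

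The omission errs in the unsafe direction. Appendix E has a column for SL-401 dosing decisions, and Sections 7.5.5.1.2 and 7.5.5.1.4 send sites to it. Section 3.6.3 names CLS as the principal DLT of Study 50047, though relatively uncommon at or below the MTD, and Section 3.6.1 describes hypoalbuminemia as one of its manifestations. At stake is further exposure, within the same cycle, of a patient whom the protocol means to stop treating. This is a patient-safety point only.

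**Working it through.** The protocol states no figure to reproduce beyond its own example, so the check is to run patients through both texts.

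**Rules compared**

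- Body text (Section 7.5.5.1.3): stop for the cycle if albumin is below 3.0, or if start-of-cycle level minus current level exceeds 1.0 g/dL.
- Appendix E: resolved if albumin is at least 3.5 and the reference level minus current level is below 0.5 g/dL. Footnote 2 then allows resumption if no measures for hemodynamic instability were needed.
- Assumptions: the patient is hemodynamically stable with no other CLS element unresolved, doses remain within the first 10 days of the cycle, and the Appendix E reference is the start-of-cycle level.

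**Case 1, the protocol's own example: 4.3 to 3.2 g/dL, infused to 3.9**

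- Body text: 4.3 − 3.2 = 1.1, which exceeds 1.0. No further SL-401 in that cycle.
- Appendix E: 3.9 is at least 3.5, and 4.3 − 3.9 = 0.4, which is below 0.5. Resolved, so dosing may resume. Any value above 4.3 − 0.5 = 3.8 would do.

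**Case 2, illustrative: 4.0 to 2.8 g/dL, infused to 3.6**

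- Body text: 2.8 is below 3.0, and 4.0 − 2.8 = 1.2 exceeds 1.0. No further SL-401 in that cycle.
- Appendix E: 3.6 is at least 3.5, and 4.0 − 3.6 = 0.4 is below 0.5. Resolved, so dosing may resume.

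The texts give opposite answers in both cases. Case 1 also shows that adding a row is not enough: 3.2 g/dL lies in the 3.0 to 3.5 band as well as meeting the fall of more than 1.0, so the existing row must exclude patients who meet the stricter tier.

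**Can the situation arise?** Section 7.5.5.1 puts CLS at 3 to 8 days after the start of treatment, and Section 7.5.2 lets held doses run to Day 10, so there is a window. It is limited: in Study 50047 (Section 3.6.1) albumin reached its minimum about one week after the first infusion, around or after the last of five consecutive daily doses. The gap matters when albumin falls earlier, or when doses have already been held into Days 6 to 10.

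**Which text is stricter on hemodynamic instability?** Here the order reverses. Under Section 7.5.5.1.1, hypotension that does not respond to 1 liter of fluid and needs further measures costs that day's dose; the cycle ends only if treatment is not feasible that day and the next. Footnote 2 of Appendix E holds SL-401 for the rest of the cycle once such measures were required. Neither text is uniformly the safer one.

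**The case against.** The strongest reply is that the protocol contains no operative conflict. Section 7.5.5.1.3 is mandatory and complete without Appendix E. Section 7.5.5.1 names it, with its neighbors, "for the management of the individual symptoms of hypotension, increase in body weight, and hypoalbuminemia", and Sections 7.5.5.9 and 8.8 also send albumin questions there. The Appendix E pointers in Sections 7.5.5.1.2 and 7.5.5.1.4 concern weight gain and CLS, and the latter calls the appendix a summary. Footnote 2 is permissive, so a site that obeys the body text violates nothing. Medical Monitor consultation is advised in the stricter tier, and same-cycle resumption after CLS needs discussion with the Medical Monitor. All of this stands. It makes the fault an incomplete summary, but does not excuse a dosing table that omits a stop.

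It can also be said that the size is unproven. Section 3.6.1 mentions albumin support for patients below 3 g/dL, but in another study and without saying whether doses remained. It reports no Grade 3 or higher hypoalbuminemia; with no grade cut-points given, that does not show how many fell below 3.0 g/dL. This also stands.

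A reader might infer that the undefined pre-dose value in the albumin row means the previous day's value, so that a slow daily decline would never trigger a hold. The documents do not support that. The adjacent weight row says so when it means the day before ("A pre-dose body weight that is increased by ≥1.5 kg over the previous" day's value), and the albumin row does not. The term is loose and worth replacing, but nothing here rests on that reading.

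**Conclusion.** The point holds as a gap in Appendix E: for a hemodynamically stable patient in the stricter albumin tier who is corrected with IV albumin, the table read alone permits same-cycle SL-401 that Section 7.5.5.1.3 forbids. The protocol's own example shows it, given that the Appendix E reference is the start-of-cycle level.

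The size is small and cannot be estimated. SAP Section 3.1 gives 18 + 9 = 27 patients enrolled at database lock, which is a ceiling and not a count of patients affected. A reader might infer that patients were in fact re-dosed against the rule, or that sites are directed to do so. The documents show neither. A reader might also conclude that the body text should simply override Appendix E; that would be wrong, because footnote 2 is the stricter text on hemodynamic instability. No endpoint, DLT rule or sample size changes. The correction is worth making because it concerns a safety stop and costs almost nothing.

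**What to change.** In Appendix E:

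1. Limit the existing on-treatment albumin row to patients who do not meet the stricter tier.
2. Add a row: *albumin below 3.0 g/dL, or down by more than 1.0 g/dL from the level at the start of the cycle: no further SL-401 in that cycle*.
3. Make footnote 2 subject to that row.
4. Replace the undefined pre-dose value with the level at the start of the cycle, as in Section 7.5.5.1.3.
5. If a precedence sentence is added, state that the stricter of Section 7.5.5.1 and Appendix E applies.

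These edits help only patients still being dosed, and since the SAP already reports enrollment at database lock there may be none. For patients already treated, flag in the clinical study report any SL-401 dose given in the same cycle after the stricter threshold was met. The by-patient exposure and laboratory listings (SAP Sections 4.4.1 and 4.4.3) are enough to find them. The protocol-violation listing (SAP Section 2.2) may not be, because a site that resumed under Appendix E may not have recorded a violation.

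The cost is one row bounded, one row added, one footnote clause, one term replaced, an optional sentence, and a cross-check of listings already planned. No new data are needed.
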